11.1.3 Roles and responsibilities in safety monitoring

The roles and responsibilities of the SDMC in relation to safety monitoring include:

- Maintaining a central database management system for clinical data; and
- Providing reports of clinical data to appropriate groups such as the HVTN 140/HPTN 101 PSRT and HVTN SMB (see Section 11.1.2).

The roles and responsibilities of the HVTN CSS or HVTN Core designee in relation to safety monitoring include:

- Daily monitoring of clinical data for events that meet the safety pause and HVTN 140/HPTN 101 PSRT AE review criteria (see Section 11.4);
- Notifying CRSs and other groups when safety pauses or planned holds are instituted and lifted (see Sections 11.3 and 11.4);
- Querying CRSs for additional information regarding reported clinical data; and
- Providing support to the HVTN 140/HPTN 101 PSRT.

11.2 Safety reporting

11.2.1 Submission of safety forms to SDMC.

CRS staff must submit all safety forms (eg, Solicited AEs, Unsolicited AEs, urinalysis, local lab results, and concomitant medications) before the end of the next business day, excluding federal or bank holidays. The forms should not be held in anticipation of additional information at a later date. If additional information is received at a later date, the forms should be updated and resubmitted before the end of the next business day after receiving the new information. For the case of a longer CRS holiday closure, CRS staff must submit the data by the end of the 5th day (local time) after receiving the information even if this day is a holiday.

For example: If the CRS becomes aware of an AE on Thursday (Day 0, the first day), the CRS must submit the data by the end of the next business day, on Friday (Day 1). If there is a longer CRS holiday closure, then this AE must be reported no later than the end of day, Monday (Day 4). If Monday is a holiday as well, all safety forms still need to be submitted by the end of Monday (Day 4).

11.2.2 AE reporting

An AE is any untoward medical occurrence in a clinical investigation participant administered a study product/procedure(s) and which does not necessarily have a causal relationship with this treatment. An AE can therefore be any unfavorable and unintended sign (including an abnormal laboratory finding), symptom, or disease temporally associated with the use of an investigational study product/procedure(s), whether or not related to the investigational study

product/procedure(s). AEs include both solicited AEs and unsolicited AEs. Solicited AEs are a subset of AEs that are defined per protocol and specifically asked about for 3 full days after each study infusion. Unsolicited AEs include all other AEs that do not fit the definition of a solicited AE. See the SSP for further detail regarding Solicited and Unsolicited AEs.

The Unsolicited AE reporting period for this study comprises the entire study period for each individual participant (from study enrollment until study completion or discontinuation of the study).

All AEs are graded according to the Division of AIDS (DAIDS) Table for Grading the Severity of Adult and Pediatric Adverse Events, Corrected Version 2.1, July 2017, available on the RSC website at <https://rsc.niaid.nih.gov/clinical-research-sites/daids-adverse-event-grading-tables>, except:

- Unintentional Weight Loss is required to be reported as an AE only if it is considered to be potentially deleterious to the participant's health (see HVTN 140/HPTN 101 SSP);
- Infusion Site Erythema or Redness and Infusion Site Induration or Swelling will not consider surface area and interference with usual social and functional activities such that:
 - Grade 1 is: 2.5 to < 5 cm in diameter;
 - Grade 2 is: ≥ 5 to < 10 cm in diameter;
 - Grade 3 is: ≥ 10 cm in diameter OR Ulceration OR Secondary infection OR Phlebitis OR Sterile abscess OR Drainage;
 - Grade 4 is: Potentially life-threatening consequences (eg, abscess, exfoliative dermatitis, necrosis involving dermis or deeper tissue);
- Creatinine is required to be reported as an AE only if it is gradable per the increase from local lab ULN/reference range parameter. Do not grade elevated creatinine based on the change from the baseline parameter.
- Creatinine clearance or eGFR is required to be reported based only on the reported value or if dialysis is needed. Do not grade Creatinine clearance or eGFR based on the change from the baseline parameter.
- Ab reactions not represented in the DAIDS Table to be graded per the "infusion related reaction" row from the Common Terminology Criteria for Adverse Events (CTCAE) from the US DHHS (Version 5.0. Published November 27, 2017, available at https://ctep.cancer.gov/protocoldevelopment/electronic_applications/docs/ctcae_v5_quick_reference_5x7.pdf (see also HVTN 140/HPTN 101 SSP)).

All AEs are reported to the SDMC on the appropriate CRF. Clinic staff should evaluate every AE to determine if: (1) the AE meets the requirements for

expedited reporting to DAIDS (see Section 11.2.3); (2) if the AE meets the criteria for a safety pause/prompt AE review (see Section 11.4).

Sites are expected to notify HVTN clinical safety staff of any serious safety concern requiring their attention (Table 11-2). Telephone numbers and email addresses are found on the protocol home page on the HVTN Members' site (<https://members.hvtn.org/protocols/hvtn140-hptn101>). Concerns requiring immediate attention should be communicated by calling the clinical safety phone.

In the case of email notification, clinical safety staff will reply within one business day. Serious events that meet pause rule criteria will be addressed immediately (as outlined in Table 11-2). If email service is not available, the CRS should notify clinical safety staff of the event by telephone, and then submit CRFs.

In addition, CRS investigators are required to submit AE information in accordance with IRB/EC and any applicable RE requirements.

11.2.3 Expedited reporting of adverse events to DAIDS

Requirements, definitions and methods for expedited reporting of AEs are outlined in Version 2.0 (January 2010) of the *Manual for Expedited Reporting of Adverse Events to DAIDS* (DAIDS EAE Manual), which is available on the DAIDS RSC website at <https://rsc.niaid.nih.gov/clinical-research-sites/manual-expedited-reporting-adverse-events-daims>. The SAE Reporting Category, as defined in Version 2.0 of DAIDS EAE Manual, will be used for this study.

The internet-based DAIDS Adverse Experience Reporting System (DAERS) must be used for expedited AE (EAE) reporting to DAIDS. In the event of system outages or technical difficulties, expedited AE reports may be submitted via the DAIDS EAE form. This form is available on the DAIDS RSC website at <https://rsc.niaid.nih.gov/clinical-research-sites/paper-eae-reporting>.

For questions about DAERS, please contact [contact] or from within the DAERS application itself.

For questions about EAE reporting, please contact the DAIDS RSC Safety Office at [\([contact]\)](mailto:([contact])).

The study products for which expedited reporting are required are:

- PGDM1400LS
- PGT121.414.LS
- VRC07-523LS

While the participant is in the study, from enrollment to the end of trial participation for that participant, the SAE Reporting Category will be used.

After the end of trial participation for that participant, unless otherwise noted, only Suspected, Unexpected Serious Adverse Reactions (SUSARs) as defined in Version 2.0 of the DAIDS EAE Manual must be reported to DAIDS, if the study staff become aware of the events.

The NIAID/DAIDS will report all unexpected SAEs related to the study products observed in this clinical trial to the FDA in accordance with 21 CFR 312.32 (IND Safety Reports). In addition, the NIAID/DAIDS or designee(s) will prepare and file expedited reports to other appropriate regulatory authorities within the timelines required by pertinent national regulatory agencies.

CRS Investigators of Record (IoRs)/designees will submit AE information and any other relevant safety information to their IRBs/ECs in accordance with IRB/EC requirements.

In some cases, the PSRT or CRS may believe unblinding of the CRS PI and participant would be appropriate to facilitate the clinical management of an AE or SAE. The Ab MOP specifies procedures for emergency unblinding, and for early unblinding for medical reasons.

11.3 Safety reviews

11.3.1 Safety Considerations for Part A dose escalation

The HVTN 140/HPTN 101 PSRT will monitor participant safety data throughout the study period as described in this section. The PSRT will review safety data for all groups to determine if enrollment may commence in subsequent groups for dose escalation. In addition, the HVTN 140/HPTN 101 PSRT will consider all available safety data on the antibodies in this study, including from ongoing and concurrent clinical trials (eg, HVTN 136/HPTN 092), in determining the appropriateness of opening HVTN 140/HPTN 101 groups to enrollment throughout the course of the trial.

The trial will begin with enrollment in Part A Group 1 only. Groups 2 and 3 will be enrolled simultaneously; then groups 4 and 5 will be enrolled simultaneously. Additional participants may be enrolled in each group to ensure the availability of safety data from at least 3 participants in each group.

Enrollment will start with Group 1 and will be restricted to a maximum of 1 participant per day across all participating CRSs until a total of 3 participants have been enrolled. Enrollment will then be held. The HVTN 140/HPTN 101 PSRT will review all cumulative safety data reported, including Group 1 data through the Day 6 visit post study product administration. Upon PSRT

determination that it is safe to proceed, enrollment in both Group 2 and Group 3 will begin (see [Table 11-1](#)).

If any \geq Grade 3 AE(s) deemed related to study product are reported in Group 1, the HVTN SMB will perform an additional unblinded review of Group 1 safety data to make the final determination based on safety for proceeding to Groups 2 and 3 enrollment.

Groups 2 and 3 will be enrolled simultaneously and will be restricted to a maximum of 1 participant per day in either group across all participating CRSS until a total of 6 participants have been enrolled. Enrollment will then be held. The HVTN 140/HPTN 101 PSRT will review all cumulative safety data reported, including Groups 2 and 3 data through the Day 6 visit post study product administration. Upon PSRT determination that it is safe to proceed, enrollment in both Group 4 and Group 5 will begin (see [Table 11-1](#)).

If any \geq Grade 3 AE(s) deemed related to study product are reported in Group 2 or 3, the HVTN SMB will perform an additional unblinded review of Groups 2 and 3 safety data to make the final determination based on safety for proceeding to Groups 4 and 5 enrollment.

Groups 4 and 5 will be enrolled simultaneously and will be restricted to a maximum of 1 participant per day in either group across all participating CRSS until a total of 6 participants have been enrolled. Enrollment will then be held.

11.3.2 Safety evaluation for moving from Part A to Part B

In addition to monitoring participant safety throughout the study period, the HVTN 140/HPTN 101 PSRT will review all cumulative safety data available from Groups 1 through 5 reported through the Day 6 visit after study product administration. Based on the assessment of this safety data and all available safety data on the antibodies in this study, including from ongoing and concurrent clinical trials, the HVTN 140/HPTN 101 PSRT will make a decision regarding the appropriateness of moving to Part B. Additional participants may be enrolled in each group in Part A to ensure the availability of safety data from at least 3 participants in each group. If any \geq Grade 3 AE(s) deemed related to study product are reported in Part A, the HVTN SMB will perform an additional unblinded review of this safety data to make the final determination based on safety for proceeding to Part B.

11.3.3 Safety Considerations for Part B dose escalation

Part B will begin with enrollment in Groups 6, 7, 8 and 9 simultaneously. Group 10 will enroll last. Additional participants may be enrolled in each group to ensure the availability of safety data from at least 8 participants in Groups 6 through 9 together; or at least 3 participants in Group 10.

Enrollment in Part B begins with simultaneous enrollment into Groups 6 through 9 and will be restricted to a maximum of 1 participant per day in any group across all participating CRSs for the first 8 participants (at least 2 participants in each group). Enrollment will then be held. The HVTN 140/HPTN 101 PSRT will review all cumulative safety data available, including Groups 6 through 9 reported through the Day 6 visit post study product administration. Upon PSRT determination that it is safe to proceed, enrollment of the remaining participants in Groups 6 through 9 will reopen to enrollment without restrictions and enrollment into Group 10 will begin (see [Table 11-1](#)). If any \geq Grade 3 AE(s) deemed related to study product have been reported in Groups 6 through 9, the HVTN SMB will perform an additional unblinded review of Groups 6 through 9 safety data to make the final determination based on safety for continuing enrollment and subsequent product administrations in Groups 6 through 9 without restrictions and proceeding to Group 10 enrollment.

Group 10 will be restricted to a maximum of 1 participant per day across all participating CRSs for the first 3 participants. Enrollment will then be held. The HVTN 140/HPTN 101 PSRT will review all cumulative safety data reported, including Group 10 data through the Day 6 visit post study product administration. Upon PSRT determination that it is safe to proceed, enrollment of the remaining participants in Group 10 will reopen to enrollment without restrictions (see [Table 11-1](#)). If any \geq Grade 3 AE(s) deemed related to study product have been reported in Group 10, the HVTN SMB will perform an additional unblinded review of Group 10 safety data to make the final determination based on safety for continuing enrollment and subsequent product administrations in Group 10 without restrictions.

Table 11-1 Summary of planned safety holds and safety data reviews for dose escalations

Planned Safety Hold #	Group(s)	Timepoint/Data Reviewed	Action
Part A^a			
1	1	Begins after the 3 rd participant is enrolled (infused) and the solicited AE assessment data through the Day 6 visit is reported. Review of all cumulative safety data available for the 3 participants in Group 1 up to and including the solicited AE assessment data reported at the Day 6 visit after the study product administration.	The PSRT (+/- SMB) will decide the appropriateness of beginning enrollment in Groups 2 and 3 based on these safety data.
2	2 & 3	Begins after the 6 th participant is enrolled (infused) in either Group 2 or 3 and the solicited AE assessment data through the Day 6 visit is reported (3 participants in Group 2 and 3 participants in Group 3). Review of all cumulative safety data available, including the first 6 participants in Groups 2 and 3 up to and including the solicited AE assessment data reported at the Day 6 visit after the study product administration.	The PSRT (+/- SMB) will decide the appropriateness of beginning enrollment in Groups 4 and 5 based on these safety data.

Planned Safety Hold #	Group(s)	Timepoint/Data Reviewed	Action
3	4 & 5	Begins after the 6 th participant is enrolled (infused) and the solicited AE assessment data through the Day 6 visit is reported (3 participants each in Groups 4 and 5). Review of all cumulative safety data available for all participants in Part A and the first 6 participants in Groups 4 and 5 up to and including the solicited AE assessment data reported at the Day 6 visit after the product administration.	The PSRT (+/- SMB) will decide the appropriateness of beginning enrollment in Part B based on all available safety data from all participants included in Part A.
Part B^a			
4	6, 7, 8 and 9	Begins after the 8 th participant is enrolled (infused) and the solicited AE assessment data through the Day 6 visit is reported (at least 2 participants in Groups 6 through Group 9). Review of all cumulative safety data available, including the first 8 participants in Groups 6 through Group 9 up to and including the solicited AE assessment data reported at the Day 6 visit after the first study product administration.	The PSRT (+/- SMB) will decide the appropriateness of continuing enrollment and subsequent product administrations in Groups 6 through 9 without restrictions, and beginning enrollment into Group 10 based on all available safety data.
5	10	Begins after the 3 rd Group 10 participant is enrolled (infused) and the solicited AE assessment data through the Day 6 visit is reported. Review of all cumulative safety data available, including the first 3 participants in Group 10 up to and including the solicited AE assessment data reported at the Day 6 visit after the first study product administration.	The PSRT (+/- SMB) will decide the appropriateness of continuing enrollment into Group 10 without restrictions based on these safety data.

^aAdditional participants may be enrolled in each group to ensure the availability of safety data from at least 3 participants in each group.

11.4 Safety pause and prompt PSRT AE review

When a trial is placed on safety pause, all enrollment and study product administration with the product related to the event that triggered the pause will be held until further notice. The AEs that will lead to a safety pause or prompt HVTN 140/HPTN 101 PSRT AE review are summarized in [Table 11-2](#). Study product administrations may be suspended for safety concerns other than those described in the table, or before pause rules are met, if, in the judgment of the HVTN 140/HPTN 101 PSRT, participant safety may be threatened. Criteria for an individual participant's departure from the schedule of study product administrations are listed in [Section 7.3](#).

Table 11-2 AE notification and safety pause/AE review rules

Event and relationship to study products	Severity	CRS action ^a	HVTN LOC action ^b
SAE, related	Grade 5 or Grade 4	Phone immediately, email and submit forms immediately	Immediate pause
SAE, not related	Grade 5	Phone immediately, email and submit forms immediately	Immediate PSRT notification
SAE, related	Grade 3, 2, or 1	Email and submit forms immediately	Immediate PSRT notification and prompt PSRT AE review to consider pause
AE ^c , related	Grade 4 or 3	Email and submit forms immediately	Immediate PSRT notification and prompt PSRT AE review to consider pause

^a Phone numbers and email addresses are found on the Protocol home page on the HVTN Members' site (<https://members.hvtn.org/protocols/hvtn140-hptn101>).

^b HVTN CSS or HVTN Core designee

^c Does not include subjective Solicited AEs (infusion site pain and/or tenderness, fatigue/malaise, myalgia, arthralgia, chills, headache, nausea (unless IV rehydration required), non-exertional dyspnea, generalized pruritus, local pruritus [SC infusion only], facial flushing, and unexplained diaphoresis).

For all safety pauses, HVTN LOC notifies the HVTN 140/HPTN 101 PSRT, HVTN Regulatory Affairs, DAIDS Pharmaceutical Affairs Branch (PAB), DAIDS Regulatory Affairs Branch (RAB), DAIDS Safety and Pharmacovigilance Team (SPT), and participating CRSs. When an immediate safety pause is triggered, HVTN LOC notifies the SMB.

Once a trial is paused, the HVTN 140/HPTN 101 PSRT reviews safety data and decides whether the pause can be lifted or permanent discontinuation of study product administration is appropriate, consulting the SMB if necessary. HVTN LOC notifies the participating CRSs, HVTN Regulatory Affairs, DAIDS PAB, DAIDS RAB, and DAIDS SPT of the decision regarding resumption or discontinuation of study product administrations. Based on the HVTN 140/HPTN 101 PSRT assessment, DAIDS RAB notifies the FDA as needed.

If an immediate HVTN 140/HPTN 101 PSRT notification or prompt HVTN 140/HPTN 101 PSRT AE review is triggered, HVTN Core notifies the HVTN 140/HPTN 101 PSRT as soon as possible during working hours (local time)—or, if the information was received during off hours, by the morning of the next workday. If a prompt HVTN 140/HPTN 101 PSRT AE review cannot be completed within 72 hours of notification (excluding weekends and US federal holidays), an automatic safety pause occurs.

The HVTN and HPTN require that each CRS submit to its IRB/EC and any applicable RE protocol-related safety information (such as IND safety reports, notification of study-product holds due to the pause rules, unanticipated problems involving risks to participants or others, and notification of other unplanned safety pauses). CRSs must also follow all applicable RE reporting requirements.

In addition, all other AEs are reviewed routinely by the HVTN 140/HPTN 101 PSRT (see Section 11.5.2).

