7.3 Participant departure from study product administration schedule or withdrawal (Part B)

This section concerns an individual participant's departure from the study-product administration schedule. Pause rules for the trial are described in Section [11.4](#).

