7.3.3 Discontinuing study product administration for a participant

Under certain circumstances, an individual participant's study product administrations will be permanently discontinued. Specific events that will result in stopping a participant's study product-administration schedule include:

- Co-enrollment in a study with an investigational research agent (rare exceptions allowing for the continuation of study product administrations may be granted with the unanimous consent of the HVTN 140/HPTN 101 PSRT)
- Clinically significant condition (ie, a condition that affects the immune system or for which continued study product administrations and/or blood draws may pose additional risk), including but not limited to the following:
 - HIV infection
 - Any grade 4 local or systemic Solicited or Unsolicited adverse event (AE) that is subsequently considered to be related to study product administration
 - Grade 3 clinical AE that is subsequently considered to be related to study product administration with the exception of fever, vomiting, and subjective local and systemic symptoms. For grade 3 infusion site erythema and/or induration, upon review, the HVTN 140/HPTN 101 PSRT may allow continuation of study product administration
 - Any grade 3 or 4 lab abnormality confirmed by a repeated value that is subsequently considered to be related to study product;
 - SAE that is subsequently considered to be related to study product administration
 - Clinically significant hypersensitivity or mAb reaction including, but not limited to, type 1 hypersensitivity reaction, urticaria, or serum sickness associated with study product administration. Consultation with the HVTN 140/HPTN 101 PSRT is required prior to subsequent study product administrations following any hypersensitivity reaction associated with study product administration
- Investigator determination in consultation with Protocol Team leadership (eg, for repeated nonadherence to study staff instructions)

Participants discontinuing study product for reasons other than HIV infection should be counseled on the importance of continuing with the study and strongly encouraged to participate in follow-up visits and protocol-related procedures per the protocol for the remainder of the trial, unless medically contraindicated (see HVTN 140/HPTN 101 SSP).

Participants diagnosed with HIV infection during the study should be encouraged to participate in follow-up visits as indicated in Section [9.12](#).

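### Table 11-2 footnote c has no grade limit, so a related, non-serious Grade 4 subjective solicited AE triggers no mandatory prompt PSRT review

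*Protocol*

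**What the plan says.** Table 11-2 (protocol Section 11.4) sorts events by seriousness, relatedness and grade. A related SAE of Grade 4 or 5 pauses the trial at once. A related SAE of Grade 1 to 3, or a related AE of Grade 3 or 4, leads to immediate PSRT notification and a prompt PSRT review of whether to pause. If that review "cannot be completed within 72 hours of notification (excluding weekends and US federal holidays), an automatic safety pause occurs".

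Footnote c is attached to the related-AE row: "Does not include subjective Solicited AEs (infusion site pain and/or tenderness, fatigue/malaise, myalgia, arthralgia, chills, headache, nausea (unless IV rehydration required), non-exertional dyspnea". The list continues with generalized pruritus, local pruritus (SC only), facial flushing and diaphoresis. It names no grade. Section 11.4 sends every AE outside the table to routine PSRT review, which Section 11.5.2 makes weekly during the dosing phase.

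Section 7.3.3 sets the rules for permanently stopping one participant's dosing. One trigger is "Any grade 4 local or systemic Solicited or Unsolicited adverse event (AE) that is subsequently considered to be related to study product administration". The Grade 3 trigger is written "with the exception of fever, vomiting, and subjective local and systemic symptoms". A further, separate trigger is an "SAE that is subsequently considered to be related to study product administration".

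Section 11.3 sets five planned holds. At each one the PSRT reviews cumulative safety data through the Day 6 visit. If a related AE of Grade 3 or higher has been reported, the Safety Monitoring Board (SMB) also reviews the data and makes the final decision. That trigger has no exemption for subjective symptoms.

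**The concern.** It is reasonable to exempt subjective reactogenicity from prompt review at Grade 3, because such symptoms are common after infusions and a trial should not be interrupted for each one. Grade 4 is different, and the protocol treats it differently elsewhere: Section 7.3.3 drops the subjective exemption at that grade, and Section 11.3 never applies one. Footnote c is the only one of the three rules that exempts subjective symptoms at Grade 4.

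At stake is a trial-level decision. A related Grade 4 headache or non-exertional dyspnea that is not reported as serious would permanently end that Part B participant's dosing. Yet nothing would oblige the PSRT to consider promptly whether others should go on being dosed.

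Timing makes this sharper. Footnote c covers solicited AEs only. By Sections 9.8 and 11.2.2, the same symptom starting after the 3-day window is unsolicited and stays in the prompt-review row. Section 4.9 reports that in the VRC01 efficacy trials all related AEs of Grade 3 or higher were reported within three days of infusion. The exemption therefore applies in the period when such events are most likely.

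**Working it through.** The plan states no figure to reproduce. The check compares the rules and counts what falls outside the prompt-review row.

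**1. Share of solicited events excluded.**
- Section 9.8.1, systemic: temperature, malaise/fatigue, myalgia, headache, chills, arthralgia, nausea, urticaria, dyspnea, tachycardia, generalized pruritus, flushing, diaphoresis = 13.
- Section 9.8.1, local: pain/tenderness, and local pruritus (SC only) = 2.
- Section 9.8.2: erythema, induration = 2.
- Total 13 + 2 + 2 = 17.
- Footnote c lists 10 systemic + 2 local = 12, and 12/17 = 71%.
- Remaining in the row: 17 − 12 = 5 (temperature, urticaria, tachycardia, erythema, induration).
- Of the 12, nausea has a severity exception and 12 − 1 = 11 have none.

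**2. The three rules side by side, for a related, non-serious subjective solicited AE.**

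| Rule | Grade 3 | Grade 4 |
|---|---|---|
| 7.3.3, stop this participant's dosing | Exempt | Stop |
| 11.3, SMB review at planned holds | Applies | Applies |
| Table 11-2 with footnote c, prompt PSRT review | Exempt | Exempt (except nausea needing IV rehydration) |

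The event matches neither SAE row because it is not serious, and footnote c removes it from the AE row. The daily checks in Sections 11.1.3 and 11.5.1 are keyed to the pause, prompt-review and expedited-reporting criteria, so they do not restore a prompt-review duty.

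**3. What is lost in time and obligation.** For an event in the row, the PSRT is told by the next workday morning at the latest. The 72-hour limit, with one weekend excluded, can span 3 + 2 = 5 calendar days. The weekly cycle can take up to 7. The difference in days is modest. The larger losses are the duty to consider a pause and the default pause if the review is late.

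**4. How far the planned holds reach** (counting each dosing visit as one administration).
- Planned administrations: 15 Part A × 1 + 80 Part B × 2 = 175.
- First doses gated by holds: 3 (Group 1) + 6 (Groups 2–3) + 6 (Groups 4–5) + 8 (Groups 6–9) + 3 (Group 10) = 26.
- Not gated: 175 − 26 = 149, including all 80 second doses.

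The Group 10 hold looks at cumulative data, so it would also see Groups 6–9 events reported by then, but it does not hold those doses. Within the gated stages, enrollment runs at no more than one participant a day until the stage is full. An event in the first participant could therefore be followed by up to 2, 5, 5, 7 or 2 further first doses in the same stage before the hold begins.

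**The case against.** The strongest reply is that the affected class may be close to empty. The only Grade 4 criterion that the protocol prints, for infusion-site reactions in Section 11.2.2, is potentially life-threatening, and the SAP's table titles use similar severity labels. If Grade 4 usually means serious, the SAE row catches the event and pauses the trial. This stands as a limit on frequency. It does not remove the gap: the documents nowhere say that Grade 4 implies serious, and both Section 7.3.3 and Table 11-2 list related Grade 4 AEs and related SAEs separately. That separation does not prove that non-serious subjective Grade 4 events occur, since laboratory values and other AEs could fill the category.

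Second, other safeguards are substantial. Forms are due by the next business day (11.2.1), clinical staff monitor daily (3.5), sites must raise serious safety concerns (11.2.2), and reactions greater than mild are generally seen within 48 hours (9.8). The PSRT may suspend dosing before any pause rule is met (11.4). An antibody reaction graded as an infusion-related reaction is not on the footnote list and stays in the row. For hypersensitivity, "Consultation with the HVTN 140/HPTN 101 PSRT is required prior to subsequent study product administrations following any hypersensitivity reaction". All of this stands. These measures deliver data, permit action or protect the individual, but none makes prompt PSRT review of this event mandatory. The infusion-reaction route also depends on how the site records the event.

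Third, the exemption may be deliberate, because the drafters thought about severity when they restored nausea needing IV rehydration. That is possible, but no reason is given for treating the other 11 symptoms differently at Grade 4.

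A reader might infer three stronger claims, and the documents support none of them:
- *The weekly cycle is the only fixed PSRT review left.* It is not: the planned holds are mandatory PSRT reviews with an SMB decision for exactly these events.
- *First-in-human dosing in Part A proceeds without a check.* All 15 Part A doses fall under a hold, and the contrast with Section 7.3.3 has practical effect only in Part B, where there is a second dose to stop.
- *The protocol contradicts itself.* The two rules serve different purposes and need not match. Fever, for instance, is exempt at Grade 3 in Section 7.3.3 but stays in the Table 11-2 row.

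**Conclusion.** The point holds as a narrow gap in the Grade 4 rule. Read literally, footnote c takes 12 of 17 solicited signs and symptoms out of mandatory prompt review at Grade 4 as well as Grade 3, with one severity exception. Two fixed PSRT reviews would still capture such an event: the weekly review, and the planned holds with their SMB trigger. The holds gate 26 of 175 planned administrations. For the other 149, the weekly PSRT review, SMB review about every 4 months and PSRT discretion apply.

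The conclusion assumes that a non-serious Grade 4 event can arise for at least some of the listed symptoms. The DAIDS grading table and the expedited-reporting manual would settle that, but the documents cite them without reproducing them. The 71% counts types of symptom and says nothing about event frequency, which is expected to be low. This is an inexpensive improvement to participant protection. It does not show that the monitoring plan as a whole is inadequate.

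**What to change.** Begin footnote c of Table 11-2 with *At Grade 3, does not include subjective Solicited AEs (…)*, keeping the list and the nausea exception unchanged. Every related Grade 4 AE would then bring immediate PSRT notification and prompt review, while Grade 3 reactogenicity stays exempt. The daily checks in Sections 11.1.3 and 11.5.1 refer to these criteria and would follow without an edit. Sections 7.3.3 and 11.3 need no change. Nor do the SAP listings, because SAP Section 9.2 already gives the SMB severe and life-threatening solicited AEs.

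The change is a few words in one footnote, made by any of the routes in protocol Section 13 (clarification memo, letter of amendment or full amendment). Its running cost is a few more notifications and prompt reviews, each carrying the 72-hour automatic-pause rule.
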